Objectives:	
Primary Objective:
 
 • To evaluate the efficacy of Afrezza administered at 2 different doses, combined with basal insulin, in adults 18 years and older with type 1 diabetes mellitus (T1DM) or type 2 diabetes mellitus (T2DM) as measured by: 
 ○ Mean change from baseline postprandial glucose based on self-monitored blood glucose (SMBG) from immediately before administering Afrezza (t=0; baseline) to 15, 30, 45, 60, 90 and 120 minutes after Afrezza dosing in conjunction with a standardized meal challenge 
Secondary Objective:
 
 • To evaluate the safety of Afrezza administered at 2 different doses, combined with basal insulin, in adults 18 years and older with T1DM or T2DM, as measured by: 
 ○ Event rates and incidence of Level 1 (<70 mg/dL) and Level 2 (<54 mg/dL) hypoglycemic events within the 120 minutes after Afrezza dosing ○ Event rates and incidence of severe hypoglycemic events, defined as events requiring assistance of another person to actively administer carbohydrate, glucagon, or other resuscitative actions within the 120 minutes after Afrezza dosing ○ Change in percent predicted forced expiratory volume in 1 second (FEV₁) before Afrezza dosing to 120 minutes after Afrezza dosing ○ Incidence and severity of adverse events (AEs): treatment-emergent adverse events (TEAEs), serious AEs (SAEs), and AEs of special interest (AESIs)
Study Design:	MKC-TI-191 is a Phase 4, single-arm, multicenter, proof-of-concept clinical trial evaluating the efficacy and safety of Afrezza, administered according to the current Afrezza prescribing

	
information (PI) compared to a titrated dose, in combination with a basal insulin in adult subjects (≥ 18 years of age) with T1DM or T2DM.
 
Eligible subjects will be on a stable regimen consisting of a basal-bolus insulin therapy prior to screening.
 
The study is composed of up to 4 clinic visits (screening, 2 treatment visits, and a follow-up visit):
 
• Screening (Visit 1): Informed consent will be obtained and eligibility confirmed. Eligible subjects will be enrolled at Visit 1.• Visit 2: The first dose of Afrezza will be based on the dose of subcutaneous rapid-acting insulin analog (RAA) that the subject would normally take, converted according to the guidelines provided in the current Afrezza PI. If the subject's normal RAA dose is < 4 units, the subject will be asked to consume enough nutritional shake, per their normal insulin:carbohydrate ratio, to cover an RAA dose of ≥ 4 units such that their Afrezza dose at Visit 3 is higher than the dose taken at Visit 2. After completing the standardized meal challenge, the Investigator will decide, based on the subject's glucose excursion at Visit 2, if the subject should proceed to Visit 3 where a second dose of Afrezza will be administered.• Visit 3: The second dose of Afrezza will be based on the dose of subcutaneous RAA that the subject would normally take, converted by multiplying their RAA dose by 2 and rounding down to the nearest Afrezza cartridge size.• Follow-up (Visit 4): Subjects will return for safety assessments 24 to 72 hours after their last dose of Afrezza. 
Treatment Period
 
Subjects will come into the clinic in a fasting state for Visits 2 and 3, with exception of treating hypoglycemia. Fasting will be defined as no intake of drink or food, with exception of water, for ≥ 6 hours before the clinic visit. At the beginning of each visit, before their dose of Afrezza, subjects will have FEV₁ measurements taken in the clinic.
 
Before each dose of Afrezza, subjects will be trained on proper inhalation technique with BluHale® PRO.
 
Each meal challenge will consist of 1 to 2 bottles of nutritional shake to be fully consumed within 15 minutes. The nutritional shake will contain approximately 240 calories, 41 g carbohydrate, 10 g protein, and 4 g fat per bottle. Each Afrezza dose will be administered at the start of the meal challenge.
 
The subject's SMBG value must be between 100 and 200 mg/dL without requiring a correction dose of bolus insulin in order to receive the Afrezza dose and complete the meal challenge. Subjects

--	--

	
using an insulin pump will be instructed to make sure their insulin pump is not in automated insulin delivery mode for the 3 hours before and during Visits 2 and 3. Subjects will also be instructed not to inject correction doses of bolus insulin during the 6 hours immediately preceding each Afrezza dose. If the subject requires a bolus insulin injection to correct hyperglycemia within the 6 hours prior to the scheduled visit, the meal challenge will need to be rescheduled. An SMBG measurement will be taken 15 minutes before the expected dose of Afrezza so the Investigator can assess if the subject is within the required SMBG range (100 to 200 mg/dL). If the subject's SMBG value is <100 mg/dL at the start of the visit, the Investigator can provide 15 g of fast-acting carbohydrates and remeasure SMBG after 30 minutes to determine if the subject should proceed to the meal challenge. The SMBG value obtained immediately before each dose of Afrezza (t=0) will be used to determine if the subject can proceed to the meal challenge and will serve as the baseline value for that visit.
 
Subjects will be monitored by the Investigator for at least 2 hours after administering each dose of Afrezza. The subject will be instructed not to ingest additional food for the 2 hours they are in the clinic for observation, with exception of treating hypoglycemia; any treatment for hypoglycemia (e.g., snack or glucose) will be documented.
 
Subjects will take SMBG measurements 15 minutes before their Afrezza dose and at t=0 (baseline), 15, 30, 45, 60, 90, and 120 minutes with respect to their Afrezza dose, where t=0 corresponds to the time immediately before administering their dose of Afrezza. Additional SMBG measurements may be taken per Investigator discretion.
 
Subjects will have an FEV₁ measurement after completion of each standardized meal challenge (120 minutes after the Afrezza dose) at Visits 2 and 3.
 
Follow-up Visit
 
Subjects will be asked to return to the clinic within 24 to 72 hours after their last dose of Afrezza for safety assessments, including a final FEV₁ measurement.

Planned Sample Size:	20 subjects (number of subjects to complete the study)
Medical Condition or Disease Under Investigation:	T1DM and T2DM, with no more than 50% of subjects having T2DM

Subject Selection Criteria:	Inclusion Criteria At screening: 
1. Subjects ≥18 years of age at the time of signing the informed consent form2. Clinical diagnosis of T1DM or T2DM (per the Investigator) and on a stable basal-bolus insulin regimen Exclusion Criteria At screening: 
1. History of asthma, chronic obstructive pulmonary disease, or any other clinically important pulmonary disease (e.g., cystic fibrosis, bronchopulmonary dysplasia), use of any medications to treat such conditions within the last year, or significant congenital or acquired cardiopulmonary disease2. History of serious complications of diabetes (e.g., active proliferative retinopathy or symptomatic autonomic neuropathy)3. On dialysis4. Respiratory tract infection within 14 days before screening (subject may return 14 days after resolution of symptoms for rescreening)5. Treatment with any investigational drug in the past 30 days or an investigational device in the past 2 weeks6. Any disease other than diabetes or initiation of any new medication that, in the judgment of the Investigator, could have a direct impact on glycemic control during the study7. Use of antiadrenergic drugs (e.g., beta blockers and clonidine)8. Any concurrent illness (other than diabetes mellitus) not controlled by a stable therapeutic regimen9. History of a significant eating disorder (e.g., anorexia or bulimia nervosa)10. Current drug or alcohol abuse or a history of drug or alcohol abuse that, in the opinion of the Investigator or the Sponsor, would make the subject an unsuitable candidate for participation in the study11. History of smoking (includes cigarettes, cigars, pipes, vaping devices, and marijuana) in the 6 months before screening12. Female subject who is pregnant, breastfeeding, intends to become pregnant, or is of child-bearing potential and not using adequate contraceptive methods as required by local regulation or practice (may include sexual abstinence)13. An event of severe hypoglycemia, as judged by the Investigator, within the 90 days before screening
-----------------------------	---

	
14. An episode of diabetic ketoacidosis requiring hospitalization within the 90 days before screening
 
15. Exposure to AfreZZa in the 30 days before screening

Study Treatment(s):	All subjects will receive AfreZZa in this study.
Test Product, Dose, and Mode of Administration:	
Test product: AfreZZa® [insulin human] inhalation powder
 
Active ingredient: Human insulin, recombinant DNA origin
 
Dose regimen: Individualized
 
Mode of Administration: Oral inhalation

Basal Insulin Therapy Dose, and Mode of Administration:	
Basal insulin analog: The subject's personal basal insulin. The dose and type of basal insulin should not be changed between Visits 1 and 3.
 
Dose regimen: Individualized
 
Mode of Administration: Subcutaneous injection or via pump. Note: Pumps cannot be in automated insulin delivery mode for the 3 hours before or during Visits 2 and 3.

Duration of Treatment:	Two individual doses of AfreZZa will be administered during this study, during Visits 2 and 3, with a standardized meal challenge.
Criteria for Evaluation:	
This study will evaluate the efficacy and safety of AfreZZa administered according to new dosing guidelines, combined with basal insulin, based on the endpoints outlined below:
 
Efficacy Endpoint
 
 Change in SMBG from immediately before administering the dose of AfreZZa (t=0; baseline) to 15, 30, 45, 60, 90 and 120 minutes after AfreZZa dosing 
Safety Endpoints
 
 Event rates and incidence Level 1 (<70 mg/dL) and Level 2 (<54 mg/dL) hypoglycemic events Event rates and incidence of severe hypoglycemic events, defined as events requiring assistance of another person to actively administer carbohydrate, glucagon, or other resuscitative actions Incidence and severity of AEs: TEAEs, SAEs, and AESIs Change in FEV₁ from t=0 to 120 minutes after AfreZZa dosing
Statistical Methods:	
Sample Size Determination
 
Twenty subjects are planned to complete the study. Subjects who do not complete the study may be replaced. The sample size of 20 subjects was not determined using statistical methods, but rather was chosen based on clinical considerations.
 
Analysis Populations

	
All subjects in the clinical study who receive a dose of AfreZZa will be included in analyses.
 
Analysis of Efficacy Endpoints
 
SMBG values will be summarized by visit. A summary table with descriptive statistics (n, mean, median, standard deviation, minimum, and maximum) by time point relative to AfreZZa dosing will be provided. SMBG data will also be presented graphically.
 
Analysis of Safety Endpoints
 
The incidence of hypoglycemia (total, nocturnal, and severe) and number of hypoglycemic episodes will be summarized. Summary tables providing frequency counts and the percentage of subjects within each category will be provided for Level 1 hypoglycemia (SMBG <70 mg/dL) and Level 2 hypoglycemia (SMBG <54 mg/dL). Exposure-adjusted incidence rates and exposure-adjusted event rates will be calculated and summarized. The number and percentage of subjects with TEAEs will be tabulated by system organ class and preferred term by relationship to treatment and by severity.
 
A summary table by study visit with descriptive statistics for FEV₁ at all time points will be provided. The FEV₁ data will also be presented graphically.

--	---

TABLE OF CONTENTS

SIGNATURE PAGE	2
SYNOPSIS.....	3
TABLE OF CONTENTS.....	9
TABLES	11
LIST OF ABBREVIATIONS AND DEFINITIONS OF TERMS.....	12
1 INTRODUCTION	14
1.1 Background	14
1.2 Study Rationale.....	14
1.3 Risks and Benefits.....	15
2 STUDY OBJECTIVES.....	16
2.1 Primary Objective	16
2.2 Secondary Objective	16
3 INVESTIGATIONAL PLAN.....	17
3.1 Overall Study Design and Plan	17
3.2 Study Duration.....	17
3.3 Selection of Study Population.....	17
3.3.1 Inclusion Criteria	18
3.3.2 Exclusion Criteria	18
3.3.3 Removal of Subjects from Therapy or Assessment.....	19
3.3.4 Replacement of Subjects.....	20
3.4 Treatments.....	20
3.4.1 Details of Study Treatments and Storage Conditions	20
3.4.2 Dosage Schedule	21
3.4.3 Treatment Assignment.....	21
3.4.4 Drug Packaging and Blinding.....	22
3.4.5 Drug Inventory and Accountability	22
3.4.6 Treatment Compliance.....	22
3.4.7 Prior and Concomitant Illnesses and Treatments.....	22
3.5 Assessments	23
3.5.1 Schedule of Assessments	23

3.5.2	Study Procedures	25
3.5.3	Procedures for Subjects Who Prematurely Withdraw from the Study	30
3.5.4	Efficacy Assessment	30
3.5.5	Safety Assessments	30
3.5.6	Appropriateness of Measurements.....	32
4	ADVERSE EVENT REPORTING.....	33
4.1	Definitions and Criteria.....	33
4.1.1	Adverse Events	33
4.1.2	Serious Adverse Events	33

Enrollment: The date when the subject has consented to participate in the study and eligibility criteria are met.

Start of the study: The study starts on the date that the informed consent form is signed for the first subject.

End of the study: The study ends with the last visit of the last subject participating in the study.

1 INTRODUCTION

1.1 Background

Diabetes constitutes one of the fastest growing global health emergencies. The prevalence of type 1 diabetes mellitus (T1DM) and type 2 diabetes mellitus (T2DM) are rising, with nearly half a billion people living with diabetes worldwide ([IDF 2019](#)). Among adults aged 20-79 years, an estimated 463.0 million adults worldwide have diabetes (~9.3% of all adults in this age group).

In both T1DM and T2DM, the therapeutic objective is to optimally control blood glucose levels and this objective is fundamentally the same in all subjects with diabetes, with individual circumstances and needs dictating what those optimal levels should be. In order to delay or prevent complications associated with diabetes, it is critical that patients adhere to their diabetes treatment regimen. Among patients treated with a multiple daily injection regimen of insulin, 1 in 5 (~20%) mealtime injections are intentionally missed, leading to challenges in achieving effective glycemic control ([Peyrot et al. 2010](#)). Reasons for omitting insulin injections include interference with daily activities, injection pain, and embarrassment.

Technosphere® Insulin inhalation powder (TI inhalation powder) provides an alternative to injectable insulin. TI inhalation powder and the Gen2 Inhaler were approved as Afrezza® (insulin human) inhalation powder and Afrezza Inhaler by the United States Food and Drug Administration (FDA) on 27 June 2014 to improve glycemic control in adult patients ≥ 18 years of age with diabetes mellitus and has been registered by the Brazilian Health Regulatory Agency (ANVISA) as of 03 June 2019. Afrezza is an ultra-rapid-acting insulin that is administered by oral inhalation using a breath-powered inhaler. Afrezza particles have a median diameter of approximately 2 to 2.5 μm , a size appropriate for inhalation into the lung. Following inhalation, Afrezza particles dissolve immediately at the physiologic pH of the lung, and insulin is absorbed systemically. After administration of Afrezza in adults, the maximum serum insulin concentration occurs in approximately 12 to 15 minutes (versus 45 to 60 minutes for a rapid-acting insulin analog [RAA] via subcutaneous [SC] route) and returns to near baseline levels in approximately 180 minutes (versus about 5 hours for RAA) ([Afrezza IB 2021](#)).

This unique ultra-rapid time-action profile allows for simpler and more flexible mealtime dosing, lessens the potential for interprandial hypoglycemia, and enables additional postprandial dosing to decrease mealtime glycemic excursions, when needed, based on the patient's self-measured glucose levels.

1.2 Study Rationale

The current study aims to evaluate 2 different doses of Afrezza in adults ≥ 18 years of age. Subjects will administer an Afrezza dose based on the current prescribing information (PI) with a meal challenge, and then proceed to a second meal challenge where a second Afrezza dose will be administered based on the subject's RAA dose multiplied by 2 and rounded down to the nearest Afrezza cartridge size, subject to Investigator discretion.

Pooled Afrezza trial data suggests that subjects achieve similar glycemic control with a dose ratio of 1.5- to 2-fold the equivalent unit value of a SC insulin analog in head-to-head comparisons (Kendall et al. 2020, Grant et al. 2019). Thus, the Sponsor has chosen to evaluate 2 different doses of Afrezza to assess whether a higher dose results in improved postprandial glucose control.

1.3 Risks and Benefits

A clear benefit of Afrezza is fewer injections compared to subjects using RAAs injected subcutaneously.

The following safety risks have been identified through evaluation of all currently available data with Afrezza:

Important identified risks

- Bronchospasm in subjects with underlying chronic obstructive lung disease
- Severe hypoglycemia
- Hyperglycemia during initiation of treatment due to inadequate conversion of RAA dose

Important potential risks

- Diabetic ketoacidosis (DKA)
- Hyperglycemia during acute illness or change of treatment
- Lung cancer: Data are insufficient to determine whether Afrezza has an effect on lung or respiratory tract tumors. In subjects with active lung cancer, a prior history of lung cancer, or in subjects at risk for lung cancer, the Investigator considers whether the benefits of Afrezza use outweigh this potential risk.

Further information on the benefits and risks of Afrezza are provided in the Investigator's Brochure (IB) ([Afrezza IB 2021](#)).

2 STUDY OBJECTIVES

2.1 Primary Objective

The primary objective of this study is:

- To evaluate the efficacy of Afrezza administered at 2 different doses, combined with basal insulin, in adults 18 years and older with T1DM or T2DM as measured by:
 - Mean change from baseline in postprandial glucose based on self-monitored blood glucose (SMBG) from immediately before administering the dose of Afrezza (t=0; baseline) to 15, 30, 45, 60, 90 and 120 minutes after Afrezza dosing in conjunction with a standardized meal challenge

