3.4.4 Drug Packaging and Blinding

This is an open-label clinical study. Neither clinical site personnel nor subjects will be blinded to treatment.

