5.2 Statistical Considerations

Any deviations from the analyses described below will be documented prior to database lock, which will be described in the clinical study report.

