5.2.11 Efficacy Analyses

SMBG values will be summarized by visit. A summary table with descriptive statistics (n, mean, median, standard deviation, minimum, and maximum) by time point relative to AfreZZA dosing will be provided. SMBG data will also be presented graphically.

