6.8 Publications and Disclosure Policy

This clinical study will be registered on ClinicalTrials.gov no later than 21 days after the first subject is enrolled, in compliance with applicable regulatory requirements.

As a multicenter trial, the Sponsor intends to publish clinical data from all centers participating in the investigation. Authorship and manuscript composition will reflect joint cooperation between multiple investigators, sites, and the Sponsor's personnel. Authorship will be established before writing of the manuscript.

In conformity with International Committee of Medical Journal Editors ([ICMJE 2019](#)) recommendations, investigators whose contribution consists solely in the collection of data will not be named individually as authors. Rather, those investigators may be included in a collective authorship (e.g., "Clinical Investigators") or acknowledged individually with their contribution(s) specified.

Individual investigators and/or their associates subsequently may publish additional findings of this study in scientific journals or present them at scientific meetings, provided that the Sponsor is given ample opportunity to review and authorize the disclosure of data for any proposed abstract, manuscript, or slide presentation before its submission. This review is required to ensure that the Sponsor authorizes the presentation of the data prior to disclosure.

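### The plan names no single measure and no within-subject contrast to answer its own dose question, so the headline result can be chosen among six time points after the data are seen

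*Combined protocol and SAP*

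**What the plan says.** **The question.** Section 1.2 says two doses were chosen "to assess whether a higher dose results in improved postprandial glucose control". That is one comparative question. Section 3.1 likewise describes the label-based dose as being compared with a titrated dose.

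**The objective.** Section 2.1 opens "To evaluate the efficacy of Afrezza administered at 2 different doses, combined with basal insulin" and is measured by mean change in SMBG from the pre-dose reading "to 15, 30, 45, 60, 90 and 120 minutes after Afrezza dosing in conjunction with a standardized meal challenge". The Synopsis (Criteria for Evaluation) gives the same six readings as the efficacy endpoint. No time point is marked as primary, and no peak, area or average is defined.

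**The analysis.** Section 5.2.11 summarizes SMBG values by visit, with a descriptive table "by time point relative to AfreZZA dosing will be provided. SMBG data will also be presented graphically". It names no change-from-baseline statistic, no difference between visits, no interval and no test. Section 5.2.4 includes every subject who receives a dose.

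**Control over later changes.** Section 3.4.4 states "Neither clinical site personnel nor subjects will be blinded to treatment". Section 5.2 states "Any deviations from the analyses described below will be documented prior to database lock", and adds that they will be described in the clinical study report. Section 5.2.1 places database lock at study completion.

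**The concern.** Six readings at two visits give 12 mean changes or six between-dose contrasts. These can disagree: a larger dose could lower glucose at some times and make no difference, or look worse, at others. The plan then has no rule for saying whether the higher dose did better.

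The between-dose contrast is itself missing. Under 3.1 the Investigator decides, from the Visit 2 glucose excursion, who goes on to Visit 3. Because 5.2.4 keeps everyone dosed, the Visit 2 summary can include subjects who have no Visit 3. Setting the two by-visit means side by side can therefore compare different groups, and it does not give the spread of the within-subject difference.

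With open-label data and an analysis that may be altered until after the last visit, the choice of headline is unprotected. At stake is an overstated benefit of the higher dose, or a report that cannot answer the question the study was set up to ask.

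**Working it through.** **Inputs from the document**
- Six post-dose readings: 15, 30, 45, 60, 90 and 120 minutes (2.1).
- n = 20 completers, not statistically determined (5.2.3). There is no power, alpha, SD or effect size to reproduce.

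**Assumed inputs** (the document gives neither)
- Correlation between two contrasts: rho^(|difference in minutes|/30), with rho from 0.6 to 0.9.
- SD of the Visit 3 minus Visit 2 difference at one time point: 40 mg/dL, with 30 to 60 as a range.

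**Step 1. Standard error of one contrast.** SE = SD/√n = 40/√20 = 8.94 mg/dL. For SDs of 30 and 60 it is 6.71 and 13.42 mg/dL.

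**Step 2. Average of the best of six when the doses do not differ.** Six correlated standard normal contrasts were simulated, 400,000 draws per row, and the one most favorable to the higher dose was kept.

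| rho per 30 min | Mean of best of six (SE units) | × 8.94 mg/dL |
|---|---|---|
| 0.6 | 0.88 | 7.9 |
| 0.7 | 0.78 | 7.0 |
| 0.8 | 0.65 | 5.8 |
| 0.9 | 0.47 | 4.2 |

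A measure fixed in advance averages 0 in the same setting. With the other SDs the range is 0.47 × 6.71 = 3.2 to 0.88 × 6.71 = 5.9 mg/dL (SD 30), and 0.47 × 13.42 = 6.3 to 0.88 × 13.42 = 11.8 mg/dL (SD 60).

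**Step 3. A different correlation structure.** With equal correlation among all six readings and n = 20 (100,000 trials), the best of six averages 0.90, 0.70 and 0.40 SE at correlations 0.5, 0.7 and 0.9. The result does not hinge on the structure in Step 2.

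**Step 4. Which single summary.** Change at t=0 is zero, so the trapezoidal weights on the six readings are 15, 15, 15, 22.5, 30 and 15 minutes, which sum to 112.5. The first four carry 67.5/112.5 = 60% of the weight, against 4/6 = 67% in a plain mean. Under the Step 2 correlations the two summaries correlate 0.992 to 0.999. Scaled so that weights sum to 1, their SDs relative to one time point are nearly equal: 0.76 to 0.94 (time-weighted) and 0.757 to 0.935 (plain mean). Dividing the area by 120, as a mean over 0 to 120 minutes requires, gives 0.72 to 0.88. That further drop is rescaling by 112.5/120 = 0.9375, which shrinks a constant effect equally, so it is not a gain in precision.

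**The case against.** The strongest reply is that this is a small, descriptive proof-of-concept study. It plans no test, alpha or interval, and for an ultra-rapid insulin the time profile is itself a legitimate result. All six time points will be tabulated and graphed (5.2.11), individual data will be listed (5.2.1), and deviations must be described in the study report (5.2). A favorable time point would appear beside the other five. All of this stands, and it limits the point to choice of headline. It does not supply a measure that answers the question in 1.2, nor the paired difference.

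Three stronger readings are tempting, and the documents do not support them.

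- **Inflated type I error.** In the Step 2 model, the chance that at least one contrast exceeds 1.96 in the favorable direction is 9.8% to 5.8%, against 2.5% for one fixed measure. That matters only if nominal tests are added; the plan contains none.
- **Late registration as a way to hide the outcome.** Section 6.8 allows registration "no later than 21 days after the first subject is enrolled", and a subject's participation lasts about 2 weeks, so the earliest subjects could finish first. But 21 days is an upper limit within a study of about 3 months (3.2), and registering the endpoint as written would leave the choice of measure just as open.
- **A plain average of the six would fail because four readings fall in the first hour.** Step 4 shows that it behaves almost identically to the time-weighted mean. Fixing one summary in advance matters far more than which of the two is chosen.

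**Conclusion.** The concern holds in a limited form. The plan asks one comparative question, offers six equal-ranking readings per visit, and defines neither a deciding measure nor a within-subject between-dose contrast. Open-label data and a late lock allow the headline to be chosen after the results are known.

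If the best of six were presented as the result and the doses did not differ, the average overstatement would be about 0.5 to 0.9 SE, or 4 to 8 mg/dL at a paired SD of 40 mg/dL and n = 20. The correlations and the SD are assumptions. The figure is also conditional on that conduct: a reader might infer that a single best time point will be reported, but nothing in the document says so.

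This should be changed, but it does not invalidate the study. One summary would let the plan give one answer. It would not make the contrast a clean dose effect: visit order is fixed, and only subjects whom the Investigator advances have both visits.

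**What to change.** In 2.1 and 5.2.11, before the first Visit 2 (which 3.5.2.1 allows to be combined with screening):

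1. Name one primary summary per subject and visit, such as the time-weighted mean change in SMBG over 0 to 120 minutes: the trapezoidal area of change from t=0, divided by 120. A plain mean of the six changes would serve nearly as well.
2. Make the headline descriptive result the paired Visit 3 minus Visit 2 difference in that summary, with a confidence interval, in subjects with both visits. State how many subjects received Visit 2 only.
3. Keep the six time points, in table and graph, as the supporting profile.
4. In 5.2, require that any analysis change made after data have been seen is labeled post hoc in the study report.
5. Reconcile 3.5.4.1, which omits the 15-minute reading, with 2.1, the Synopsis, Table 2 (footnote e) and the Visit 2 and Visit 3 dosing sections, which include it. The summary needs a settled set of readings.

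The cost is protocol wording, one derived variable and one paired analysis, all from readings already collected. No dose, visit or clinical rule changes. The downside is that an effect confined to one time point becomes supportive rather than the headline.
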